7.1 Screening Period

The screening period will take place within 4 weeks of Day 1, except where otherwise noted. Assessments not completed within the specified interval must be repeated.

7.2 Screening Identification Numbers

Study site personnel will maintain a screening log for all potential study participants, and will assign a screening identification (ID) number in consecutive order as listed on the screening log. The screening ID number will be used on all study forms and laboratory specimens throughout the study.

A new screening ID number will be assigned to a patient who is rescreened after originally failing to meet study eligibility.

For patients who provide informed consent and subsequently do not meet eligibility criteria, or withdraw consent, study site personnel will ensure that the source record includes appropriate documentation, such as eligibility criteria reviewed, protocol procedures performed, and reason for screen failure.

7.3 Study Procedures

Table 1. Schedule of Activities

Study Period or Visit	Screening	Baseline	Treatment Period (16 weeks)\		Follow-up	
			Pre-Treatment	weekly Traning	Midpoint Assessment	Study FU
Study Week Window (Weeks)	NA	-4 to -1	-2 to -1	±1	8	17
	NA	NA	±1		±1	±2
General Activities						
Informed Consent		X				
Medical History	X					
Height, Weight	X	X			X	X
Vital Signs	X				X	X
Performance Status (ECOG) ⁴	X					
Concomitant Medications	X					
Randomization ⁵		X				
Study-Related End Points						
Cardiopulmonary exercise test (CPET) ^{4,5}		X			Arms A and C only	X
One repetition maximum (1RM) ⁶		X			Arms B and D only	X
Functional performance measures		X				X
Resting left ventricular ejection fraction		X				X
Pulmonary Function Test		X				X
Post-exercise left ventricular ejection fraction		X				X
DEXA (body composition)		X				X
Regional arterial stiffness		X				X
Flow Mediated Dilatation		X				X
Patient-reported outcomes (lifestyle questionnaire)		X				X
Training			X			
Complete Blood Count (CBC)		X			X	
Research Blood draw		X			X	

[1] Testing slot availability must be taken into consideration when scheduling study follow-up visits. Visits may be split across the window to permit for

completion of all study-related assessments.

[2] Performance status by Eastern Cooperative Oncology Group (ECOG) scoring.

[3] Randomization should be performed on or up to 2 weeks prior to Day 1, but only after eligibility is confirmed.

[4] Must be assessed within 4 weeks of randomization to confirm eligibility. All potential participants will perform a second CPET at baseline to account for potential learning effects and variability to account for the presence of significant, and potentially clinically important, variability in CPET procedures (VO₂peakmeasurement),

[5] CPET at midpoint is for patients randomized to Arms A and C only.

[6] One repetition maximum at midpoint is for patients randomized to Arms B and C only.

7.4 Blinding

This study is open label. All patients and study exercise physiologists monitoring exercise training sessions will be unblinded to treatment allocation (due to the nature of aerobic training interventions, neither patients nor study personnel can be blinded to treatment allocation). Nevertheless, all study investigators will be blinded to intervention allocation. Only the trial statistician and the data monitoring committee will have access to unblinded data.

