9.4 Aerobic and Resistance Training Dose Modification

Vital signs will be monitored during intervention sessions to ensure participant safety. Vital sign changes that are outside the expected range of the intervention will be monitored by the exercise physiologist. The exercise physiologist will use clinical discretion to determine if a modification to the prescription or termination of the session is required.

All modifications will be source documented and recorded in the study database, including the modification reason, how the session was modified, and clearance obtained, as appropriate.

Participants requiring consistent modification of the planned prescription will be reviewed by the study PI and exercise physiologists to determine appropriate action (e.g., early study withdrawal, physiological re-evaluation).

Final determination of the intensity and duration of the session against the planned session goals will be conducted by the supervising exercise physiologist following the session and will be source documented.

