Exercise testing-related events were operationalized as any event occurring during this procedure. SAEs will be defined as the occurrence of any of the following: (1) significant angina, (2) sustained ventricular tachycardia, (3) myocardial infarction, (4) external defibrillation or implantable cardioverter-defibrillator discharge, (5) syncope, (6) provision of cardiac life support medications, (7) direct admission to emergency room, or (8) death. A positive test was defined as identification of any of the following ECG changes: (1) significant ischemic changes in ECG during exercise or recovery or (2) development of exercise induced bundle branch block. Criteria for ischemic changes in ECG included 0.1 mV deviation of the ST segment horizontal to or away from the baseline isoelectric line at 0.08 seconds after the J-point in the absence of significant resting ST-T abnormalities or left bundle branch block. ST segment changes toward the isoelectric line will not be considered positive, regardless of the magnitude of change. If the baseline ECG reveals a J-ST segment depression >0.05 mV, a "double criteria" (an additional 0.2 mV) of ST depression will be required with the appropriate horizontal or downsloping morphology to qualify as a positive test.

Clinical exercise physiologists within the ExOnc at MSK will perform all cardiopulmonary exercise tests. All personnel are trained to read (but not interpret) exercise ECG's and are trained in Advanced Cardiovascular Life Support (ACLS). All tests will only be conducted when physician coverage on the clinical floor is available.

All cardiopulmonary exercise testing will be conducted in Cardiology Service space either at Main Campus or in the Outpatient Facility on 53rd Street, or at the Sidney Kimmel Center for Prostate and Urologic Cancers, on designated ExOnc equipment specifically designated for research purposes.

If any ECG abnormalities are observed either prior to, during, or after the exercise test, all procedures will be immediately stopped. At this point, a cardiologist will be asked to review the ECG to determine the appropriate course of action. The participant will not be allowed to leave the facility until such an examination has been performed by the physician. All events will be recorded in the participants REDCAP. The participants attending oncologist will be informed of this event (by email) within 12 hours of the event.

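### Section 7.4 says all investigators are blinded, which the PI's own duties contradict; separately, no readable section protects the effort-dependent Week 17 CPET from tester knowledge of the arm

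*Combined protocol and SAP*

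**What the plan says.** Section 7.4 (Blinding) makes four statements in sequence:

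- The trial is described as open label.
- Patients, and the physiologists who oversee training, are named as knowing the arm. The reason given is that "neither patients nor study personnel can be blinded to treatment allocation".
- The sentence that follows says the opposite for one group: "Nevertheless, all study investigators will be blinded to intervention allocation".
- Access to data by arm is then limited to the statistician and the monitoring committee.

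Section 9.4 gives the PI a role in individual training plans: "Participants requiring consistent modification of the planned prescription will be reviewed by the study PI and exercise physiologists to determine appropriate action". Early withdrawal is one of the actions it lists. Section 17.2 requires the PI's signature on SAE reports, which must state how the event relates to the intervention.

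On measurement, Section 9.2 has an exercise physiologist supervise every session. Section 12.1 says: "Clinical exercise physiologists within the ExOnc at MSK will perform all cardiopulmonary exercise tests". The same section runs the test to exhaustion or a symptom-limited peak and accepts it if any one of four criteria is met, one of which is a rating of perceived exertion.

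**The concern.** There are two separate problems.

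The first is accuracy. A publication that follows Section 7.4 would describe the trial as investigator-blinded. If the PI learns participants' arms in the ordinary course of the protocol, that description is wrong, and readers would credit the trial with a safeguard it does not have.

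The second is measurement of the primary endpoint. VO2peak depends on how hard the participant is willing to push. A tester who knows the arm may, without intending to, encourage exercise-arm participants more than stretching participants. Baseline CPETs are done before randomization, so tester knowledge can affect the Week 17 value but not the baseline value. Adjusting for baseline VO2peak, as Section 14.2.1 plans, would not remove such a difference.

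**Working it through.** **Text comparison: investigator blinding.**

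1. Section 7.4 says study personnel cannot be blinded, and its next sentence says all investigators will be. The two can be reconciled only if the investigators are kept away from anything that shows the arm.
2. Section 9.4 does not keep them away. Sections 9.2.1 to 9.2.4 prescribe cycling (Arm A), weight machines (B), both modes (C) and stretching (D). Reviewing a modified prescription therefore shows the arm. The review covers only participants who need consistent modification, but a single such review is enough to make a statement about all investigators untrue.
3. Section 17.2 points the same way, less directly: judging relationship to the intervention normally requires knowing what the intervention was.
4. Section 15.2 files the allocation email in the participant's case report form, and no rule keeps investigators from seeing it.

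**Text comparison: who tests.**

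1. Section 7.4 names the physiologists who monitor training as unblinded.
2. Section 12.1 assigns all MSK CPETs to exercise physiologists of the same program.
3. No section that can be read keeps a physiologist from testing a participant he or she trained, or sets out standard encouragement.
4. Section 10.1 repeats the CPET at the end of Week 8 only in Arms A and C, so whoever runs that test learns part of the allocation.

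**Scale, for illustration only.** The plan gives no figure for tester bias, so there is none to reproduce.

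Inputs: SD of change 3.0 mL/kg/min (Section 14.1); 40 per arm, of whom 16, 17 and 16 in Arms A, B and C are to be enrolled at MSK (Section 1.0). Assumption: encouragement adds 0.3 to 0.6 mL/kg/min (0.1 to 0.2 SD) to each affected exercise-arm participant and nothing in Arm D, with no true effect.

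- Standard error of a difference = 3.0 × √(2/40) = 0.671.
- Mean shift = assumed shift × affected patients / 40.
- λ = mean shift / 0.671.
- Error rate = P(Z > 1.96 − λ) + P(Z < −1.96 − λ).

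| Assumed shift | Affected of 40 | Mean shift | λ | Two-sided 5% error becomes |
|---|---|---|---|---|
| 0.3 | 16 | 0.120 | 0.179 | 5.4% |
| 0.3 | 17 | 0.128 | 0.190 | 5.4% |
| 0.6 | 16 | 0.240 | 0.358 | 6.5% |
| 0.6 | 17 | 0.255 | 0.380 | 6.7% |
| 0.3 | 40 | 0.300 | 0.447 | 7.3% |
| 0.6 | 40 | 0.600 | 0.894 | 14.5% |

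These are for one unadjusted comparison. At the first Holm threshold (0.05/3, nominal 1.67%), the same formula gives about 1.8% to 2.5% when only MSK patients are affected.

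A simulation of all three t-tests against Arm D at the first Holm step gives a 4.5% chance of at least one false positive with no bias. With the shift confined to MSK patients, this becomes 4.9% at 0.3, 5.6% at 0.5 and 9.2% at 1.0. With all 160 patients exposed to biased testing and a shift of 0.5 in Arms A to C, it is 11.7%.

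**The case against.** The strongest reply is that nothing promised has been broken for the primary endpoint. The protocol calls itself open label in both Section 4.1 and Section 7.4, discloses that patients and training physiologists know the arm, and never says the CPET tester is blinded. Investigator blinding would not have covered the testers anyway, and the PI does not run CPETs, so the PI's knowledge has no shown route to VO2peak. All of this stands. A reader might infer that the primary endpoint has lost a protection the plan claimed for it; the documents do not support that reading.

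A reader might also infer that trainers test their own participants, or that the endpoint is biased. Neither is documented. The text names one professional group for both tasks and is silent on rostering. Appendix H (Exercise Physiology Guidelines) is listed, but its text is not available here, so testing rules in it cannot be ruled out.

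The control arm is a further mitigation. Section 4.2 gives Arm D one-to-one supervised contact matched for sessions per week, session length and program length. Familiarity between trainer and participant would therefore exist in Arm D too; only encouragement that differs by arm would bias the comparison.

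Finally, the statement on who performs CPETs describes MSK. Of the 160 patients, 93 were randomized at the first site, where tester blinding is not described. The larger error rates, which assume that every patient is affected, should not be taken as the expected case.

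These replies limit the second problem. They do not rescue the investigator-blinding sentence, which Section 9.4 contradicts.

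**Conclusion.** The concern holds in two parts of unequal strength.

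The contradiction is certain and depends on no assumption: as Section 9.4 is written, the statement that all investigators are blinded cannot be true.

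The CPET exposure is a gap in the stated safeguards at Week 17, of unknown size. Under the assumed 0.3 to 0.6 mL/kg/min shift in MSK patients alone, the effect on error is small: about 5.4% to 6.7% against a nominal 5%. The range 7.3% to 14.5% applies only if all 40 patients in an exercise arm were affected. Both ranges rest on the planned SD of 3.0, 40 analyzed per arm, a normal approximation and no shift in Arm D.

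The change is worth making because it is cheap and bears on the primary endpoint and on what may be claimed for it, not because bias has been shown.

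**What to change.** 1. Replace the investigator-blinding sentence in Section 7.4 with an accurate list of who is and is not blinded, consistent with Sections 9.4 and 17.2. Do not report the trial as investigator-blinded.
2. Use one scripted set of encouragement, identical across arms, at all remaining Week 17 CPETs.
3. Where the existing roster allows, have the Week 17 CPET run by a physiologist who did not train that participant, and record each case where this was not possible. This should be a preference rather than an absolute rule, because the documents give no staffing numbers and each participant has 48 planned supervised sessions. If Appendix H already covers this, refer to it in Section 12.1.
4. Report peak RER at Week 17 by arm as a check on equal effort. The CPET already yields it.

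The cost is protocol wording, a short script, some scheduling constraint and one descriptive table. No new assessment is needed. The change cannot affect tests already completed at the first site, so the report should say that the safeguard covers only later MSK tests.

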7.5 Study Duration

The study should be accruing patients for around 24 months from the start of accrual. Patients will be followed for up to one year following the last patients last follow up appointment.

8.0 PRETREATMENT EVALUATION

After obtaining written consent and GLTEQ, all participants will be scheduled for a baseline study assessment visit by a member of the ExOnc research team. Following appropriate scheduling procedures, at the study visit, the participant will complete the following assessments prior to randomization:

1. Fasting blood draw
2. Fasting, non-invasive measurement of regional arterial stiffness and flow mediated dilation
3. Resting assessment of left ventricular function using echocardiography
4. Symptom-limited cardiopulmonary exercise test with 12-lead electrocardiography (including pulmonary function testing) and post-exercise echocardiography
5. Functional measures
6. Body composition
7. Patient-reported outcomes
8. One repetition maximum

The completion of these assessments will take approximately 3 to 4 hours and will be conducted in the ExOnc Integrative Physiology Laboratories at either: Main Campus (in Cardiology), the Rockefeller Outpatient Pavilion at 53rd Street, or the Sidney Kimmel Center for Prostate and Urologic Cancers.

The DEXA scan will be performed at either the Breast and Imaging Center (BAIC) or the Rockefeller Outpatient Pavilion.

In order to maximize internal validity of study endpoint assessments efforts will be made to ensure assessments at baseline, midpoint and follow-up are in the same order.

All baseline study assessments are described in Table 2.

Table 2. Pretreatment Evaluations (including Baseline Study Measures)

Activity/ Assessment/ Timing	Comment
------------------------------	---------

Symptom-limited cardiopulmonary exercise test (CPET) to assess peak oxygen consumption (VO2peak)	
VO2peak will be evaluated using a magnetically-braked cycle ergometer test with 12-lead ECG monitoring (Mac® 5000, GE Healthcare) performed by certified exercise physiologists.
 
Cardiopulmonary exercise testing is considered the gold standard assessment of exercise capacity and provides assessment of peak oxygen consumption (VO2peak)- Expired gases will be analyzed continuously by a metabolic measurement system (Parvo Medics TrueOne 2400). After stable resting metabolic values have been achieved (including blood pressure and heart rate), participants will begin cycling at a participant-specific designated power output for 1 minute and the power output will be increased every 1 minute until exhaustion or a symptom-limited peak is achieved measured by peak oxygen consumption (VO2peak) (mL·kg⁻¹·min⁻¹)
 
This protocol has been previously demonstrated to be appropriate for measuring VO2peak in our prior studies among cancer patients.^{36,37}
 
Acceptable test criteria for this assessment include any of the following: (1) a plateau or decrease in oxygen consumption concurrent with increased workload, 2) heartrate 220-age (±10 beats) (3) a respiratory exchange ratio =1.1, (4) volitional exhaustion, a rating of perceived exertion 18. This protocol has been previously demonstrated to be appropriate for measuring VO2peak in our prior studies of early-stage and advanced cancer patients.^{36,37}
 
The test will be terminated if any ECG abnormalities are observed.
 
Due to the presence of significant, and potentially clinically important, variability in CPET procedures (VO2peak measurement), all potential participants will perform a second CPET at baseline to account for potential learning effects and variability.³⁸ If both the first and second CPET achieve acceptable test criteria, the best test will be used.

One repetition maximum (1RM)	Participants will perform a cardiovascular warm-up on a treadmill or bicycle ergometer prior to testing for 5 minutes. After an appropriate rest period, participants will be familiarized with each of the resistance machines by performing 8-10 repetitions of a light load (~30-40% of predicted 1RM). After ~3 min of rest, participants will complete a priming load at 60-80% of estimated 1RM for 3-8 repetitions. Following 5 min of rest the participant will attempt a lift of ~90-100% of estimated 1RM through the full range of motion. After each successful performance, the weight will be increased until a failed attempt occurs. The highest weight moved once through the particular range of motion with maximal exertion will be defined as the 1RM. In order to allow for appropriate recovery and reduce the influence of fatigue, exercises will be alternated between the upper and lower body. Three to five minute rests will be given between each attempt and the 1RM will ideally be attained within 5 attempts.
Resting left ventricular function by 3-	Three-dimensional transthoracic echocardiograms will be

dimensional echocardiography (3DE)	
performed by experienced sonographers and acquired with commercially available equipment (Vivid 7 or E9, GE Healthcare, Milwaukee, WI).
 
Following completion of the 2DE, a full volume dataset will be acquired using a matrix array transducer with gated 4 beat acquisitions for assessments of left ventricular (LV) volumes by 3DE. A 3DE acquisition of the entire LV will be generally performed in <10 seconds. All assessments will be stored digitally for offline analyses performed using EchoPAC PC workstation (version BT11, GE Medical, Milwaukee, WI). Conventional 2D measurements of LV dimensions, Doppler, and diastolic function parameters will be performed and averaged over 3 cardiac cycles according to American Society of Echocardiography guidelines.⁹ ₄
 
Left ventricular volumes and left ventricular ejection fraction (LVEF) by 3DE will be determined by manipulating the full volume dataset to derive conventional apical 4-, 3-, and 2-chamber views using TomTec offline analysis software (4D LV-Function, Unterschleisheim, Germany). After selection of reference points, a 3D endocardial contour will be automatically generated and manual adjustment will be performed as necessary. The resultant end-diastolic (EDV) and end-systolic volumes (ESV) will be used to calculate LVEF.⁴²

Post VO_{2peEJ}< left ventricular function by 2-dimensional echocardiography (2DE)	
Upon completion of the cardiopulmonary exercise test, subjects will be placed in the supine position and 2DE grayscale images will be obtained in the apical 4-, 3-, and 2-chamber views. Wall motion scoring index (WMSI) will be calculated at rest and post-exercise using the 17 segment model by adding the individual segment scores (1 = normal; 2 = hypokinesia; 3 = akinesia; 4 = dyskinesia) and dividing by number of segments scored.³⁹ 2D LV volumes and LVEF will be calculated offline using the modified Simpson's biplane method. Cardiac output will be calculated as the product of LV stroke volume and heart rate, indexed to body surface area (BSA).

Regional arterial stiffness	
Conduit regional artery stiffness of the entire aorta will be assessed non-invasively by measuring carotid-femoral pulse wave velocity (PWV) using 2 hand-held tonometers (SPT-301 Millar Instruments, Houston, TX).
 
Carotid and femoral artery waveforms will be recorded independently, as long as the heart rate and rhythm are consistent throughout, with the mechanotransducers directly applied to the skin over the greatest area of pulsation. Twenty consecutive reproducible beats will be collected at both sites, with a concurrent electrocardiograph to obtain R-R intervals. Pulse transit time will be determined as the difference in time from R interval to systolic upstroke at each location. Systolic upstroke will be determined by identifying the foot or "notch" of the blood pressure waveform. This will be done by applying a band pass filter between 5-30 Hz, selecting the minimum value of the filtered signal.

	
Pulse distance will be determined using anthropometric measuring tape subtracting the distance from carotid measurement to sternal notch from the distance from sternal notch to femoral pulse measurement. This method has been shown to be the optimal non-invasive measurement compared to invasive measure. PWV will then be determined by taking the pulse transit time/distance.

Flow Mediated Dilatation	
Peripheral artery flow-mediated dilatation (FMD) will be performed on one arm with the subject in a supine position with the forearm extended and slightly supinated.
 
A rapid inflator blood pressure cuff will be placed on the forearm just distal to the antecubital crease and the brachial artery will be imaged using high-resolution B-mode ultrasound and a 7.5MHz linear array transducer (Terason, t3200). Ten-second r-wave triggered digital clips (artery diastole) will be captured at baseline (following 10min of supine rest), during five minutes of forearm occlusion, and a 120 sec r-wave triggered digital clip will be captured beginning at cuff deflation (hyperemia) as previously described.⁷
 
Offline analysis using specialized software (Brachial Tools, Medical Imaging Applications, Illinois) will permit for identification of peak dilation and dilation at specific pre-specified time points (60, 120 sec).³⁷

Dual energy x-ray absorptiometry (DEXA) to assess body composition	
Body fat percentage, and lean and fat body mass will be assessed by dual energy x-ray absorptiometry using a Lunar Prodigy multiple detector fan-beam densitometer (GE Medical Systems, Madison, WI). After calibration with an anthropomorphic phantom, single-beam, whole-body scanning will be employed on supine-positioned subjects. Data will be obtained from each scan for fat and lean body mass expressed to the nearest tenth of a gram (and percent) for the total body region, as well as in defined body zones (e.g., legs, trunk and arms).
 
Each participant's Baseline and Follow Up DEXA assessments will be performed on the same machine as best possible.

Patient-reported outcomes (via questionnaire)	
Patient-reported outcomes will be assessed using a patient-administered questionnaire to assess quality of life, fatigue, pain, and sleep quality.
 
Quality of Life (QOL) will be assessed by the Functional Assessment of Cancer Therapy (FACT) scale developed for the assessment of patient symptoms and QOL in breast cancer patients.³⁸
 
Fatigue will be assessed using the 13-item FACIT-Fatigue scale for the assessment of fatigue in cancer patients.³⁹
 
Pain will be assessed using the 10-item Brief Pain Inventory (BPI) which was designed to measure multiple clinically relevant aspects of pain such as pain intensity

	
and interference from pain in cancer populations.^{4u}
 
Sleep Quality will be assessed by the Pittsburgh Sleep Quality Index (PSQI).⁴¹
 
Medical Outcomes Trust Short Form Health Survey (SF-36): The SF-36 is a psychometrically robust self-report questionnaire that measures general health-related quality of life in 8 domains of health: physical functioning (SF-36 PF), role limitations caused by physical health (role-physical), bodily pain, general health perceptions, vitality, social functioning, role limitation due to emotional problems (role-emotional) and mental health.⁴²

Fasting research blood draw	Blood collection should take place prior to the initiation of any study related interventions, whenever possible.
Pulmonary function testing	Pulmonary function will be determined using standard spirometry. All measures will be performed in a sitting position according to the American Thoracic Society guidelines. ⁵³
Functional performance measures	
Assessment of functional measures will include the performance of the following tests:
 
• Short Physical Performance Battery (SPPB): The SPPB is a brief performance-based functional mobility measure that includes measures of standing balance, usual pace walking speed, and ability and time to rise from a chair 5 times.• Six-Minute Walk Test (6MWT): The 6MWT is a valid responsive, interpretable self-paced test that quantifies functional exercise capacity in terms of the distance walked in six minutes.• Chair-stand test: Chair-stand test (number of sit to stands a subject can complete in 30 seconds) will be used as a measure of functional lower body strength.• Timed Up and Go (TUG): TUG is a timed measure of balance and functional mobility. The test requires the patient to rise from a standard armchair, walk 3 meters at a comfortable pace, walk back to the chair, and sit down.

Following the completion of all baseline assessments, patients will be randomly assigned to one of the four study arms.

